In order to use an RCT to assess the effectiveness of the PIUO Pathway, we need a large number of participants - more than can be found in one center. Therefore, with the help of colleagues we will recruit children from across Canada into the study. Children will be recruited at 4 participating centers where Site Leads familiar with our population and the issue of PIUO are located: BC Children's Hospital (BCCH), Vancouver ([name]), Alberta Children's Hospital (ACH), Calgary ([name]), Hospital for Sick Children (HSC), Toronto ([name]) and Children's Hospital of Eastern Ontario (CHEO), Ottawa ([name]).

RECRUITMENT

Participants

Children aged 6 months to 18 years with SNI (from any cause) with unexplained pain and irritability and whose cognitive or communication impairments prevent determination of pain location, cause, and type will be eligible to participate.

Eligibility

Inclusion criteria: Eligible children will have cognitive impairment or be non-verbal and have severe levels of disability equivalent to Gross Motor Functional Classification System (GMFCS) scores of 3, 4 or 5. Eligible children will score ≥ 3 on two scales administered via an Eligibility Screening (Appendix 2) that measure persistence and distress level the child is experiencing as well as identifies the type of pain and irritability as PIUO – with no obvious cause or explanation. The score of ≥ 3 on the scale measuring pain persistence and distress level confirms that the child is experiencing pain and irritability more than “a little” on “some days”. The parent will confirm that the experience of pain and irritability has been present within the last month of the eligibility screening, although we recognize that some children will have experienced PIUO for much longer. The score of ≥ 3 on the pain identification scale indicates that the child has unexplained pain and irritability (as opposed to, for example, ongoing pain due to a known cause such as esophagitis). Parents should have sufficient English/French language skill, or have access to assistance, to participate in the clinic visits and complete survey tools. The Child will also have a score of 4 or 5 on the Communication Function Classification System (CFCS).

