Exclusion criteria: Children will be excluded if they are not within the specified age range; have the communication capabilities and cognitive development to localize their pain or have an explained and treatable cause of pain and irritability.

Randomization

Participants will be randomized to start the PIUO Pathway or to the waitlist control arm. The list of random allocations will be generated at WCHRI's DCC centre using REDCap. An automated audit trail of all transactions, including assigned study identification number, treatment allocation, and time and date of the transaction will be recorded by REDCap. Randomization will be stratified by site and using permuted blocks of sizes 2 and 4.

Sample Size

The sample size calculation was based on the anticipated treatment difference between PIUO Pathway arm and waitlist control arm in the period between 8 and 12 weeks. As stipulated in the section on primary outcomes (page 12) a patient will be considered a success if they are judged to be in the lowest two pain categories (A or B) on consecutive visits beginning at weeks 8 or 10. We anticipate that a 25% response to treatment during this period would be the minimal required to be viewed as clinically important, and we believe that a 25% response rate is achievable. The response rate during this period in the waitlist control is assumed to be zero, although we have set it at 5% to be cautious. To achieve 80% power using a two-tailed $\alpha=0.05$ using the Fisher's exact conditional test for comparing proportion, we require 57 patients per group. The Site Leads confirm that this number is readily obtainable within the proposed timeline.

Recruitment Procedures

It is anticipated that the same recruitment procedures will be followed at all four sites. However, minor modifications may be necessary for compliance with the individual ethics board at those institutions. Recruitment will be amongst outpatients, however if a child is hospitalized after enrolment, s/he can remain on the study.

Families will be made aware of the study via the following two channels:

1. A letter (Appendix 7) will be sent on behalf of the Principal Investigator, by the Site Leads to respective community pediatricians and sub-specialty clinics where children with SNI often receive care (e.g., Neurology, Complex Care, Orthopaedics, etc.). The letter invites them to refer patients to the study.

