- The Pain Survey tool will measure pain and irritability persistence and distress level throughout the study. A quick, two question assessment, the pain survey is taken from the Washington group Extended Question Set on Functioning (WGES-F) and is adapted here for use in children. The pain question set has been shown to have good validity and is able to correlate with other pain measurements in adults.⁵⁰ Although this two-question pain survey is simple, it is sufficiently informative so as to be of use in describing a child's pain, without unduly burdening parents with an overload of questions every two weeks. Pain Surveys will be completed biweekly throughout the Study as described below. Participants will be deemed to have had a positive outcome if they score in category A or B (see Appendix 5) on two consecutive visits. We will compare those who have a positive response on weeks 8, 10 and 12 between intervention and waitlist group.
- PROMIS-57 (Patient Reported Outcomes Measures Information System) is a multi-dimensional tool that will assess parents' well-being in the face of their child's chronic pain and irritability. This assessment is one of the two primary outcome of this project. PROMIS-57 was developed as part of an initiative of the US Department of Health and Human Services to establish a common set of patient reported outcome measures (www.healthmeasure.net). The PROMIS tools are found to be valid and reliable. There is a Canadian PROMIS coordinator as well, and support is available for translation and adaption to the REDCap database which we will be using. There are several PROMIS tools assessing various elements of adult and child health and well-being. The PROMIS-57 tool assesses across the following domains: physical function, anxiety, depression, fatigue, sleep, social participation, and pain interference in daily activity. While we cannot attribute all changes in quality of life to improvement in the child's pain and irritability, we will analyze to look for high degrees of correlation.

ANALYSIS

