The primary analytic strategy is based on the assumption that it will take some time after the screening period (weeks 0-2), the onset of randomization (week 2-3) and the Pathway initiation (weeks 4-10 in the Pathway group) for the intervention to have its full impact. As well, to determine the impact relative to the Waitlist group, the comparison must take place before the intervention is delivered to the Waitlist group (i.e. prior to cross-over). Thus, the primary analysis will focus on the measurements taken at weeks 8, 10, and 12.

The primary outcome is a change in Pain Survey score, moving a child from any high pain and irritability score (C, D, and E), to a low score (A, B) for 2 continuous reporting periods. A level B score ("little pain" on "some days") is clinically acceptable in this health challenged popula-

tion, although not ideal. Previous work has indicated that complete absence of pain is not always achievable in this population.^{3, 33}

The primary comparison will use a Fisher's exact test to compare the proportion of patients achieving a successful outcome in the period starting between week 10 and 12. We will also perform an adjusted analysis using logistic regression and treating the baseline category as a covariate.

In addition, we will compare the Pathway groups on each domain of the PROMIS-57 instrument at week 10. The dependent measures will be the domain scores at week 10, the covariates will be the scores at baseline of each domain, and the independent variable will be the Pathway group. Multiple linear regression will be used to evaluate the intervention differences. In the primary analysis, all participants measured on week 10 will be included. Multiple imputation will be used in a sensitivity analysis to include participants without measures on week 10.

As a secondary analysis, we will determine whether the intervention had an effect in the Waitlist group by comparing their measurements on the pain outcomes at week 14, 16 and 18 with their week 10 measurements (just before they cross over to the Pathway).

DATA STORAGE

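### The primary success rule is stated with and without a high-pain starting category, and nothing confirms that category at the baseline Pain Survey

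*Protocol*

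**What the plan says.** Three sections of the protocol define success on the Pain Survey.

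- Sample Size: "a patient will be considered a success if they are judged to be in the lowest two pain categories (A or B"). Two visits in a row must qualify, the first of them at week 8 or 10. No baseline condition.
- Data Collection Tools, Primary Outcomes: "Participants will be deemed to have had a positive outcome if they score in category A or B" on two consecutive visits. No baseline condition.
- Analysis: the outcome is a change, "moving a child from any high pain and irritability score (C, D, and E), to a low score (A, B"), for two reporting periods in a row. The assessment that supplies the starting category is not named.

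Eligibility requires a score of at least 3 at the screening, which is described as confirming pain above a little on some days. Analysis describes level B in almost those terms. On timing, Eligibility adds: "The parent will confirm that the experience of pain and irritability has been present within the last month of the eligibility screening". The Pain Survey itself covers the last two weeks (Study Sequence). It is given at the baseline interview, after consent and before random assignment, but no category is required there. Analysis places screening in weeks 0-2 and randomisation in week 2-3.

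**The concern.** A child who screens in with high pain but is at A or B on the baseline survey, and stays there, is a success under Sample Size and Primary Outcomes. Under Analysis the same child cannot be one if the baseline survey is the starting point, yet can be one if the screen is. The primary endpoint of that child is therefore not fixed.

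The gap between screen and baseline is two to three weeks. The protocol describes the pain as occurring in episodes, so some drift is plausible. Few successes are expected: at 57 per arm, 0.25 × 57 = 14.25 in the Pathway arm and 0.05 × 57 = 2.85 in the waitlist arm. Reclassifying two or three children could change a Fisher result, and a rule chosen after the data are seen would be open to challenge.

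**Working it through.** **Inputs from the protocol (Sample Size).** "To achieve 80% power", "using a two-tailed $\alpha=0.05$ using the Fisher's exact conditional test for comparing proportion"; Pathway 25% ("a 25% response to treatment during this period would be the minimal required to be viewed as clinically important"); waitlist expected at zero, "although we have set it at 5% to be cautious"; 57 per group. Study Design gives 120 in total, taken here as 60 per arm.

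**Inputs not in the protocol (assumptions).** f is the share of each arm at A or B at baseline, shown at 5% and 10%. s is the share of those children who are still at A or B in the primary window, in both arms alike, shown from 50% to 90%.

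**Step 1: the plan's own figure.** Enumerated power of the two-sided Fisher's exact test for 25% v 5% first reaches 80% at 55 per arm (80.1%). It is 82.0% at 57 and 84.5% at 60. The stated 57 is reproduced to within two patients.

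**Step 2: success rates when some children start at A or B.** Let c be the waitlist success rate among children at C-E.

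- Status rule (A or B, no starting condition): Pathway (1 − f) × 0.25 + f × s; waitlist (1 − f) × c + f × s.
- Change rule (from C-E at baseline): Pathway (1 − f) × 0.25; waitlist (1 − f) × c.

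Example with f = 5% and c = 5%. Under the status rule at s = 50%, Pathway is 0.95 × 0.25 + 0.05 × 0.5 = 26.25% and waitlist is 0.95 × 0.05 + 0.05 × 0.5 = 7.25%. At s = 90% they are 28.25% and 9.25%. Under the change rule they are 23.75% and 4.75%.

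**Step 3: exact power with c = 5% (the planning value).** Ranges run from s = 50% to s = 90%.

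| f | n per arm | Status rule | Change rule |
|---|---|---|---|
| 0% | 57 | 82% | 82% |
| 5% | 57 | 72-68% | 79% |
| 10% | 57 | 63-56% | 76% |
| 0% | 60 | 85% | 85% |
| 5% | 60 | 75-70% | 82% |
| 10% | 60 | 65-58% | 79% |

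**Step 4: the same at 57 per arm with c = 0% (the protocol's expectation).** Under the status rule power is 96-93% at f = 5% and 89-81% at f = 10%. Under the change rule it is above 99% in both cases.

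**Step 5: where the rules separate.** At f = 0 they are identical. The difference arises only through children who change category between screen and baseline. At f = 5% that is about 0.05 × 57 = 2.85 children per arm.

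**The case against.** The strongest reply is that the entry criterion already reconciles the wording. Every eligible child appears to be above level B at screening, so the change wording in Analysis can be read as restating the entry state. This narrows the conflict considerably but does not close it, because the screen comes two to three weeks before randomisation and the later survey carries no category requirement. The match between a screening score of 3 and category C is itself inferred from similar descriptions, since Appendices 2 and 5 are not available. Nor is the one-month period stated to be the recall window of the scored scale, so the contrast with the survey's two weeks should not be pressed.

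A second reply concerns power. The 5% waitlist rate is already a margin above an expected zero. Adding A/B children on top of a full 5% is the more cautious case, and Step 4 shows power above 80% without it. The plan also randomises 120 rather than 114. Both points stand.

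A reader might infer three stronger things that the protocol does not support:

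- *That the trial is underpowered.* The share at A or B at baseline is not given, and the loss depends on it and on the waitlist rate.
- *That the comparison is biased.* Assignment follows baseline, so such children are balanced in expectation.
- *That the adjusted logistic regression fails through separation.* That model is supplementary to Fisher's test. The problem needs baseline category to be entered as a factor, which is not stated, and strata with no successes carry no information on the treatment effect.

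**Conclusion.** The inconsistency in the primary success rule is real and needs no assumption to see. Its reach is limited to children who fall to A or B between the phone screen and the baseline survey. For them the protocol neither requires C-E, nor names the reference assessment, nor says how they are counted.

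The consequence is dilution of unknown size. On the cautious assumptions (5% at A or B, half to nine-tenths staying there, 5% waitlist response among C-E children) the status rule costs 10 to 14 percentage points of power at 57 per arm and the change rule about 3. At 60 per arm the change rule still gives 82%. With the expected 0% waitlist response, no scenario shown falls below 80%. A definite loss of power therefore cannot be claimed. The point is worth correcting because it concerns the primary endpoint and the correction is cheap.

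**What to change.** Use one sentence in Sample Size, Primary Outcomes and Analysis: success is category A or B on two consecutive visits in the primary window, in a child who was in C, D or E on the baseline Pain Survey. Confirm C-E on that survey before randomisation. A child at A or B is deferred and may be screened again. The two rules then coincide and the planning rates apply to everyone randomised.

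If the sponsor prefers not to add the check, it should name the baseline survey as the reference and fix in advance how a child at A or B at baseline is counted.

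The cost is protocol wording and one check on data already collected. The downside is that a few children with fluctuating pain are deferred. The weeks that make up the primary window are also worded differently in Sample Size and Analysis; that is a separate matter to settle when the sentence is written.

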Interventions for resolving PIUO are time and resource intensive. They require a focused approach to assessing all the underlying possibilities for the PIUO and addressing each potential source of pain one at a time. Tackling PIUO requires systematic, comprehensive, process-oriented thinking applied by an interdisciplinary team with flexibility in terms of approach and time. There have been recommendations in the literature about how to approach the problem of PIUO in children with SNI, but these recommendations have never been subjected to systemic evaluation as complex interventions, for example by following an integrated clinical pathway.^{12,37} Integrated clinical pathways (also called "care pathways" or "critical pathways") are structured, sequenced approaches guiding the delivery of healthcare, often with a multidisciplinary perspective.³⁸ They provide algorithms to be followed in the assessment and treatment of conditions, but are not intended to be rigidly followed; instead, integrated clinical pathways delineate a foundation for a clinician's approach to a complex problem, thereby avoiding inefficiencies in evaluation or resource use. Integrated clinical pathways are a form of Complex Interventions and have been developed for sickle cell pain,³⁹ childhood asthma,⁴⁰ appendicitis,⁴¹ autoimmune conditions,⁴² inborn errors of metabolism,⁴³ and cerebrospinal fluid shunt management.⁴⁴ Despite their complexity, integrated clinical pathways are appropriate interventions for evaluation by Randomized Controlled Trial (RCT).⁴⁵ RCTs of integrated clinical pathways have been proposed and/or completed for complex, multi-factorial patient problems including lung disease, heart failure, gastrointestinal surgery, stroke, and hip fractures.^{38,46-48}

In this study, we will use a waitlist-controlled RCT design, with 120 children randomized to PIUO Pathway or waitlist (standard care) treatment arms. This design was chosen strategically, with consideration of both the special pediatric population being studied and the ethical inappropriateness of randomly assigning children to a placebo group when pain is the target condition.

The Study Sequence, Events Grid and a detailed depiction of the PIUO Pathway are shown in Appendix 1, 1a and 1b.

STUDY SITES

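### Fisher's exact test for the primary pain comparison is valid but conservative at this size; Boschloo's exact test would add about 3 points of power at 60 per arm with no extra patients

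*Protocol*

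**What the plan says.** The Analysis section of the protocol fixes the test for the Pain Survey success proportion: "The primary comparison will use a Fisher's exact test to compare the proportion of patients achieving a successful outcome". A logistic regression adjusted for baseline category is planned in addition.

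The Sample Size section plans for the same test. For the Pathway arm, "we believe that a 25% response rate is achievable"; the waitlist rate "is assumed to be zero, although we have set it at 5% to be cautious". The result is stated as "using the Fisher's exact conditional test for comparing proportion, we require 57 patients per group", for 80% power at two-tailed 0.05. The Study Design section plans for more than the required 114, "with 120 children randomized to PIUO Pathway or waitlist (standard care) treatment arms". The Randomization section ("Randomization will be stratified by site and using permuted blocks of sizes 2 and 4") and the equal group sizes imply 1:1 allocation, so 60 per arm.

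The protocol mentions no unconditional exact test, mid-p version or other adjustment for Fisher's conservatism.

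**The concern.** Fisher's test is calibrated separately for each possible total number of successes. When that total is small, only a few tables are possible, and the attainable p-values jump from well above 0.05 to well below it. The plan itself expects few successes: 0.25 × 60 = 15 in the Pathway arm and 0.05 × 60 = 3 on the waitlist, with a stated belief that the waitlist rate is zero. In that range much of the 5% error allowance goes unused.

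An exact unconditional test can use more of the allowance while still keeping the error at or below 5%. What is at stake is power on the pain comparison. Some results that would be significant under an equally exact test will be reported as non-significant.

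**Working it through.** **Inputs (protocol).** Success rates 25% and 5%, two-sided 0.05, 80% power, Fisher's exact test, 57 per group (Sample Size); 120 randomized (Study Design), taken as 60 per arm.

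**Method.** With n per arm, enumerate all (n+1)² tables (x successes on Pathway, y on waitlist).
- Fisher's two-sided p-value is the sum, given the total m = x + y, of the hypergeometric probabilities no larger than that of the observed table.
- Power = Σ Bin(x; n, 0.25) · Bin(y; n, 0.05) over the rejected tables.
- Actual type I error is the same sum with a common rate π in both arms. Its maximum is taken over a grid of π from 0.001 to 0.999.
- Boschloo's test uses Fisher's p-value as its statistic. It raises the cut-off to the largest value at which the maximum type I error stays at or below 0.05.

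**Step 1: the plan's own figure.** Exact Fisher power is 79.1% at 54 per arm, 80.1% at 55 and 82.0% at 57. The stated 57 is reproduced to within two patients per arm and meets its target.

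**Step 2: why Fisher is conservative here.** With 60 per arm and m = 5, the most extreme split is 5 against 0. Its p-value is 2 × C(60,5)/C(120,5) = 2 × 5,461,512/190,578,024 = 0.057. So with five successes or fewer in the whole trial, Fisher cannot reject whatever the split. At a common rate of 5% the expected total is only 120 × 0.05 = 6.

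**Step 3: size and power.**

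| | Fisher, 57 | Boschloo, 57 | Fisher, 60 | Boschloo, 60 |
|---|---|---|---|---|
| Cut-off on Fisher p | 0.050 | 0.074 | 0.050 | 0.066 |
| Error at π = 5% | 0.95% | 2.5% | 1.05% | 2.7% |
| Error at π = 10% | 2.1% | 4.0% | 2.2% | 3.4% |
| Error at π = 25% | 3.1% | 4.6% | 3.0% | 4.1% |
| Maximum error | 3.2% | 4.9% | 3.5% | 4.9% |
| Power, 25% vs 5% | 82.0% | 87.6% | 84.5% | 87.4% |

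Because the cut-off is only relaxed, Boschloo's rejection region contains all of Fisher's at both sizes. The gain at 25% vs 5% is 87.4 − 84.5 = 2.9 points with 60 per arm and 87.6 − 82.0 = 5.6 points with 57. Fisher first passes 80% power at 55 per arm and Boschloo at 51.

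**Step 4: tables that change verdict with 60 per arm** (Fisher p, Boschloo p): 15 vs 6 (0.053, 0.035); 12 vs 4 (0.058, 0.038); 9 vs 2 (0.053, 0.035); 7 vs 1 (0.061, 0.042); 5 vs 0 (0.057, 0.038).

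**Step 5: if some children cannot be analysed.** The protocol gives no attrition rate, so these losses are assumptions. With 10% lost (54 per arm), power is 79.1% for Fisher and 85.5% for Boschloo. With about 13% lost (52 per arm) it is 77.3% and 83.9%; with 20% lost (48 per arm), 72.2% and 77.7%.

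**The case against.** The strongest reply is that nothing is wrong. The trial is sized for the test it will use, so the conservatism was paid for in the 57 per group, and the power obtained exceeds the target. If the waitlist rate really is zero, Fisher's power with 60 per arm is 99.9%. All of this stands, and it is why the point is one of efficiency.

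Four stronger readings are tempting, and the documents do not support them.

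- A reader might infer that Boschloo gives the same guarantee at no price. It does not. Fisher holds 5% for every total number of successes; Boschloo holds it only on average over totals, under independent binomial sampling. With 60 per arm, Boschloo's error given the total is 5.7% at 5 successes, 6.1% at 8 and 6.2% at 23. With 57 per arm it is 7.4% at 13. Whether conditional control matters when the total is not fixed by design is a long-standing dispute, but it is something that Fisher provides.
- A reader might infer that this is the trial's only deciding comparison. The Primary Outcomes section presents PROMIS-57 as a second primary outcome, so the point concerns the pain comparison only.
- A reader might take the larger gain as typical. Part of the 5.6 points at 57 per arm comes from discreteness: Boschloo's power falls to 86.0% at 58 before rising to 87.4% at 60. At the planned size the gain is about 3 points. It is larger at 20% vs 5% (62.7% to 67.9% with 60 per arm), but a 20% response lies below the 25% that the protocol treats as the smallest clinically important response.
- A reader might see the changed verdicts as important effects lost. Of the five tables listed, only 15 vs 6 has a Pathway response of 25%; in the others it is 20%, 15%, 12% and 8%.

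**Conclusion.** The point holds as a cheap improvement to a valid plan. Fisher's test leaves unused between about 1.5 points (5 − 3.5, its maximum with 60 per arm) and 4 points (5 − 1, at a common 5% rate) of the 5% error allowance. Boschloo's test recovers part of this: about 3 points of power at 25% vs 5% if all 60 per arm are analysed, and about 6 points at 57. The margin would matter most if more than a few children are lost, since Fisher drops below 80% power at 54 per arm.

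This rests on 1:1 allocation, equal analysed arms, independent binomial outcomes that ignore the site stratification, and the protocol's own success rates. The exact gain will move with the number finally analysed.

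**What to change.** In the Analysis section, before any outcome data are seen, name Boschloo's exact unconditional test at two-sided 0.05 as the primary test of the Pain Survey success proportion. State that tables are ordered by the two-sided Fisher p-value, and name the software. This matters because some software instead doubles the smaller one-sided p-value. The two versions agree when the arms are equal but can differ when they are not, and missing surveys or incomplete blocks could leave the analysed arms unequal.

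Keep 57 per group and 120 randomized; the Fisher-based calculation then becomes a conservative one. Report Fisher's p-value as supportive.

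The cost is a line or two of text, with no change to recruitment or procedures. The drawbacks are that the test is less familiar to readers and controls only the unconditional error.

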investigations and treatments for pain and irritability. These include laboratory tests, imaging, and interventional and surgical procedures that were directed towards addressing pain and irritability. We will collect consultation reports to enhance the information provided in the parent history. The results of this record will be compared with the recommendations of the PIUO Pathway in order to avoid any duplication or unnecessary repetition of assessment or treatment. Based on our previous pilot study many children will likely have had some, but not all, elements of the PIUO Pathway completed. The Study Research Nurse will mail out the Consent Form to participants and include instructions on how to answer three questionnaires that will be sent to the participant via e-mail as REDCap surveys, once consent has been obtained. The questionnaires are: The Baseline Non Communicating Children's Pain Checklist Revised (NCCPC-R), the Face, Legs, Activity, Cry and Consolability (FLACC) and the Patient reported Outcomes Measures Information System Pain Survey (PROMIS-57). A survey to obtain basic demographic information from the participating family will also be sent out via REDCap. The participant is to mail back the signed consent form in a pre-stamped return envelope.

The Study Research Nurse will meet with participants for a baseline interview, ideally at a time that coincides with other appointments at the hospital. At the baseline interview, the Study Research Nurse will administer the Health Information Form (Appendix 4), confirm the information collected from the child's health record and confirm the child's GMCFS score based on the assessment at the Eligibility Screening as well as evaluate the child's CFCS level. The Study Research Nurse will administer the Pain Survey and collect the, NCCPC-R, FLACC and the (PROMIS-57) which have been mailed out prior to the baseline interview. PROMIS-57 will be completed again at week 10 of the study and upon completion of the Pathway as well as at Follow Up 8 weeks post Pathway completion. The Pain Survey and the FLACC will be repeated at Follow Up as well.

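### The deciding pain comparison is a valid but unadjusted Fisher's exact test; stratifying that exact test by baseline pain category would be a cheap and modest gain in efficiency

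*Protocol*

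**What the plan says.** The Analysis section of the Protocol fixes the deciding test: "The primary comparison will use a Fisher's exact test to compare the proportion of patients achieving a successful outcome". Success means leaving categories C, D or E for A or B over two consecutive reports. The next sentence adds the baseline: "We will also perform an adjusted analysis using logistic regression and treating the baseline category as a covariate". That model accompanies the Fisher comparison and does not decide the trial. The Sample Size section is built on the same Fisher's test.

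The baseline category is available in time. In Study Sequence, at the baseline interview, "The Study Research Nurse will administer the Pain Survey and collect the, NCCPC-R, FLACC", and random assignment follows once the baseline is established. The Randomization section says: "Randomization will be stratified by site and using permuted blocks of sizes 2 and 4". Starting pain category is therefore not a stratification factor.

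**The concern.** Baseline and outcome are on the same scale, and success is defined by crossing a fixed line on it. A child who starts at C is nearer that line than one who starts at E, so starting category may well predict success. The Protocol treats it as relevant by naming it as the covariate in the supporting model.

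Two things follow if it is left out of the deciding test. A chance difference between arms in starting severity passes unadjusted into the deciding p-value. Any precision that the category could supply, from data already collected, is also unused.

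The supporting logistic regression does not fully fill the gap. Very few waitlist successes are expected, and the model is least stable in the case that the Protocol itself expects.

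**Working it through.** **Inputs from the Protocol.** Pathway response 25% ("we believe that a 25% response rate is achievable"). Waitlist response "is assumed to be zero, although we have set it at 5% to be cautious". Two-sided alpha 0.05, target power 80%, 57 per group, and 120 randomised (60 per arm if allocation is 1:1, which block sizes of 2 and 4 fit).

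**Step 1: the plan's own figure.** Enumerating both binomials with the two-sided Fisher p-value gives power of 80.1% at 55 per group, 82.0% at 57 and 84.5% at 60. The stated 57 is confirmed, with a small margin. Actual type I error at 57 per group is 0.0095 if both rates are 5% and about 0.031 if both are 25%, so the test is conservative.

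**Step 2: chance imbalance.** Assume one third of children start at C and ignore site blocking. The standard error of the between-arm difference in that share at 57 per arm is √(2 × 1/3 × 2/3 ÷ 57) = 0.088. A difference of 10 points or more means at least 6 children (6/57 = 10.5%). With continuity correction, z = (5.5/57)/0.088 ≈ 1.09, a two-sided probability of about 27%. Simulation gave about 28%.

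**Step 3: the supporting model.** Expected waitlist successes are 57 × 0.05 = 2.85, or 60 × 0.05 = 3. The chance of none is 0.95^57 = 5.4% (4.6% at 60). If the true waitlist rate is zero, which the Protocol assumes before setting 5% for caution, the treatment odds ratio has no finite maximum-likelihood estimate.

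**Step 4: the stratified exact test.** The statistic is the number of Pathway successes summed over baseline strata. Its null distribution is the convolution of the stratum-specific hypergeometric distributions, so it is exact given the stratum margins.

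The simulations used 6,000 trials per scenario, with C, D and E assumed equally common. Success rates by category are assumptions chosen to average 25% and 5%; for example (55 + 15 + 5)/3 = 25 and (12 + 2 + 1)/3 = 5. Results at 57 per arm, power in %:

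| Pathway C/D/E; waitlist C/D/E | Fisher | Stratified, probability rule | Stratified, twice smaller tail |
|---|---|---|---|
| 25/25/25; 5/5/5 (none) | 82.0 | 84.1 (+2.1) | 81.7 (−0.3) |
| 35/25/15; 7/5/3 (weak) | 82.3 | 85.3 (+3.0) | 82.7 (+0.4) |
| 42/23/10; 10/4/1 (moderate) | 81.5 | 86.5 (+5.0) | 83.4 (+1.9) |
| 55/15/5; 12/2/1 (very strong) | 81.0 | 89.6 (+8.6) | 87.2 (+6.2) |

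Fisher's true power is 82.0% in every row, because the overall rates do not change. The spread in that column is simulation error: √(0.82 × 0.18/6000) ≈ 0.5 point.

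At 60 per arm the probability rule gave about 84 against 86, 85 against 87, 85 against 89 and 85 against 92. The twice-the-smaller-tail rule gave 84.5 against 84.0, 84.4 against 84.7, 83.5 against 85.5 and 85.1 against 89.2 (−0.5, +0.3, +2.0, +4.1).

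**Step 5: why the two-sided rule matters.** With equal arms Fisher's null distribution is symmetric, so the two rules agree. Within strata the arms are unequal by chance, so the stratified null is asymmetric and the rules differ. In the first row category predicts nothing, so its 2-point gain under the probability rule comes from a less discrete distribution and the choice of rule. None of it comes from prognostic information.

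**Step 6: error rate.** Under the probability rule, simulated type I error of the stratified test was about 0.02 to 0.025 with both rates at 5%, and 0.035 to 0.042 with both at 25%.

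**The case against.** The strongest reply is that nothing here is wrong. A pre-specified Fisher's exact test controls type I error whatever imbalance chance produces. It matches the sample-size calculation and exceeds the stated power. The baseline category is also examined, in a pre-specified adjusted model. An unadjusted exact primary test with an adjusted companion is a common choice when few events are expected. All of this stands.

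The size of the gain is also open to challenge. It depends on the two-sided rule, and under the twice-the-smaller-tail rule it disappears when prognosis is weak. The top scenario implies a C-versus-E odds ratio in the Pathway arm of (55/45)/(5/95) ≈ 23, which is extreme. The prognostic value of category is inferred: the Pathway works by finding an undiagnosed cause, so success may depend more on whether one is found. These points stand as well, and they set the limits of the claim.

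A reader might infer that the primary analysis is biased, invalid or underpowered, or that the plan ignores baseline pain altogether. The document supports none of these. Nor does it support a guaranteed gain of several points, or a stratified test that can never fall below Fisher. A reader might also take the baseline adjustment of the PROMIS-57 regressions as evidence of inconsistency. It is not, because adjusting a continuous score is routine and says little about a sparse binary outcome.

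One reply does not hold: that the logistic regression makes the change unnecessary. With zero to three waitlist successes expected, it cannot be relied on to show what adjustment would do.

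**Conclusion.** The point holds as a modest efficiency improvement. It is not an error in the plan. The deciding test leaves out a baseline value that is measured before randomisation, lies on the outcome's own scale and is not balanced by design. The only planned adjustment for it is fragile at the expected event counts.

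At 57 to 60 per arm and 25% against 5%, stratifying the exact test adds about 2 to 3 points of power with no or weak prognostic value, about 5 with moderate and 6 to 9 with very strong, under the probability rule. Under the twice-the-smaller-tail rule the figures are about zero (−0.5 to +0.5), about 2, and 4 to 6. Type I error stays below 0.05.

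These ranges rest on an assumed category mix and prognostic strength, neither of which the Protocol gives. The stated 57 per group and 80% power are unaffected.

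**What to change.** Amend the Analysis section before outcomes are compared between arms:

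- Make the primary comparison the exact conditional test stratified by baseline Pain Survey category (C, D, E), which is the stratified form of Fisher's test.
- Name the two-sided rule in the same sentence. The probability rule is the one commonly used for Fisher's test.
- Report a baseline-adjusted difference in success proportions with its 95% confidence interval.
- Keep the unstratified Fisher's test as the supporting analysis.

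The change needs a sentence or two and no extra children, visits or data. The sample-size statement can stay: 57 per group already meets 80% with plain Fisher, and the stratified test was above 80% in every scenario tabulated under either rule. The cost is a headline test slightly less simple than one two-by-two table, with little return if starting category predicts success weakly.
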